6.5. Concomitant Therapy

Medication or therapy considered necessary for the subject's welfare may be given at the discretion of the Investigator. Subjects may continue participation in the study if the instituted medication or therapy will not interfere with the evaluation of the study medication. Whenever possible, medications should be administered in dosages that remain constant throughout the study. Any treatment other than the study medication during the study duration will be considered as a concomitant treatment. The information of concomitant treatment must be recorded in the subject's source documents and on the eCRF.

• Concomitant medication: name of medication, route of administration, treated eye(s) (if applicable), dose, frequency, indication, start date, and stop date.

• Concomitant therapy: name of therapy, treated eye(s) (if applicable), indication, start date, and stop date.

6.5.1. Collection of Prior and Concomitant Medication Information

At Screening, information on prior and concomitant medications taken within the previous 90 days will be collected and to satisfy assessment of study Inclusion and Exclusion Criteria. At each study visit, subjects should be questioned concerning any new medications or changes in their current medications since their previous study visit and the information should be recorded in the eCRF. For all medications, the generic name, indication, route of administration, frequency, dose, start date, and stop date (if applicable) will be collected; for combination products, the brand name will also be documented.

- Any history of ocular surgery (including ocular laser surgery) in either eye or plan of ocular surgery (including ocular laser surgery) during the course of the study.
- Prior invasive therapy for presbyopia (*e.g.*, ciliary body electrostimulation, corneal implants).
 - Prior medical therapy for Presbyopia (*e.g.*, supplements, miotic medications, training exercises) within 30 days of Visit 1 (Screening)
 - Subjects with prior non-surgical optical correction (*e.g.*, corrective eyeglasses) are eligible for the study
- Subjects with any history or current use of contact lenses, or plan of use during course of study
- Current or planned participation in any other clinical study involving an investigational product or device within 4 weeks prior to Visit 1 or at any time during this study.

6.6. Rescue Medicine

Not applicable. There are no alternative standard medicinal therapies for the condition being treated.

6.7. Dose Modification

Dose modifications are not allowed in this study.

6.8. Intervention after the End of the Study

No subsequent intervention is planned for subjects after completing the study. Standard of care will resume at the investigator's discretion.

7. DISCONTINUATION OF STUDY INTERVENTION AND PARTICIPANT DISCONTINUATION/WITHDRAWAL

7.1. Discontinuation of Study Intervention

It may be necessary for a participant to permanently discontinue (definitive discontinuation) study intervention. If study intervention is definitively discontinued, study assessments should be completed per SoA including Exit Visit. All efforts should be made to complete an early discontinuation exit visit. If study medication is definitively discontinued and the subject has an AE related to study medication, he/she will remain in the study to be evaluated until the resolution of the AE. See the SoA for data to be collected at the time of discontinuation of study intervention and follow-up and for any further evaluations that need to be completed.

Discontinuation of study intervention for any safety concern should be considered if the investigator believes that it is in best interest of the participant.

If a clinically significant finding is identified (including, but not limited to clinically significant changes from baseline in any laboratory evaluation) after enrollment, the investigator or qualified designee will determine if the participant can continue in the study and if any change in participant management is needed. Any new clinically relevant finding should be reported as an AE.

7.1.1. Temporary Discontinuation

Temporary discontinuation of study medication is not applicable in this study.

7.1.2. Rechallenge

Not applicable to this study.

7.2. Participant Discontinuation/Withdrawal from the Study

• A participant may withdraw from the study at any time at his/her own request or may be withdrawn at any time at the discretion of the investigator for safety, behavioral, compliance, or administrative reasons. This is expected to be uncommon.

- At the time of discontinuing from the study, if possible, an early discontinuation visit should be conducted, as shown in the SoA. See SoA for data to be collected at the time of study discontinuation and follow-up and for any further evaluations that need to be completed.
- The participant will be permanently discontinued both from the study intervention and from the study at that time.
- If the participant withdraws consent for disclosure of future information, the sponsor may retain and continue to use any data collected before such a withdrawal of consent.
- If a participant withdraws from the study, he/she may request destruction of any samples taken and not tested, and the investigator must document this in the site study records.

7.3. Lost to Follow up

A participant will be considered lost to follow-up if he or she repeatedly fails to return for scheduled visits and is unable to be contacted by the study site.

The following actions must be taken if a participant fails to return to the clinic for a required study visit:

- The site must attempt to contact the participant and reschedule the missed visit as soon as possible and counsel the participant on the importance of maintaining the assigned visit schedule and ascertain whether or not the participant wishes to and/or should continue in the study.
- Before a participant is deemed lost to follow up, the investigator or designee must make every effort to regain contact with the participant (where possible, 3 telephone calls and, if necessary, a certified letter to the participant's last known mailing address or local equivalent methods). These contact attempts should be documented in the participant's medical record.
- Should the participant continue to be unreachable, he/she will be considered to have withdrawn from the study.

Discontinuation of specific sites or of the study as a whole are handled as part of Section 10.1.

8. STUDY ASSESSMENTS AND PROCEDURES

8.1. Visit Details

• Study procedures and their timing are summarized in the SoA (Table 2). Protocol waivers or exemptions are not allowed.
- Immediate safety concerns should be discussed with the sponsor immediately upon occurrence or awareness to determine if the participant should continue or discontinue study intervention.
- Adherence to the study design requirements, including those specified in the SoA, is essential and required for study conduct.
- All screening evaluations must be completed and reviewed to confirm that potential participants meet all eligibility criteria. The investigator will maintain a screening log to record details of all participants screened and to confirm eligibility or record reasons for screening failure, as applicable.
- Procedures conducted as part of the participant's routine clinical management (*e.g.*, blood count) and obtained before signing of the ICF may be utilized for screening or baseline purposes provided the procedures met the protocol-specified criteria and were performed within the time frame defined in the SoA.

The primary efficacy analysis will be assessed at the 2 Month visit.

8.1.1. Visit 1 (Screening)

• Explain the purpose and conduct of the study to the subject and obtain written individual informed consent. Informed consent for the optional BOSS[™] testing must be obtained prior to lens elasticity measurement at Visit 1 (Screening). Ensure the subject understands that if he/she does not wish to participate in BOSS[™] testing that their decision will have no influence on their participation in the main study. BOSS[™] testing is only available at a subset of clinical sites.

- Prepare the list of screening/registration of subjects.
- •
- Obtain demographics.
- Obtain medications, procedures/therapies, and medical and surgical history including all lifetime ocular medical history to the extent possible, non-ocular medical history within 10 years, diagnosis, ocular surgical history, current ocular, and systemic conditions.
- Measure vital signs
- Measure height and weight

- Obtain urine and perform a urine pregnancy test, if the subject is a female of child-bearing potential.
- Instruct subject to complete clinical lab collection (urinalysis, hematology, chemistry and HbA1c). Results of clinical lab must be received and reviewed prior to Visit 2 (Baseline).
- Assess for adverse events (occurring after the signing of the informed consent)
- Assess eligibility of subject by reviewing the inclusion and exclusion criteria. A subject who does not meet eligibility criteria or will not otherwise continue in the study is considered a screen failure.
- Enter the subject information into the EDC system for Visit 1 (Screening) to obtain the subject ID

8.1.2. Visit 2 (Baseline, Day 1)

- •
- Measure vital signs
- Update concomitant medications and procedures/therapies

8.1.3. Double-Masked Treatment Period, Visit 3 (Day 7)

- Measure vital signs
- Update concomitant medications and procedures/therapies

- Update concomitant medications and procedures/therapies
- Beneficial and a second seco
 - •
- Assess for adverse events
- •

8.1.5. Double-Masked Treatment Period, Visit 5 (Month 1)

- Measure vital signs
- Update concomitant medications and procedures/therapies

•	
•	
•	
•	
•	
•	
•	Perform slit-lamp Biomicroscopy

- Measure pupil size
- Measure Intraocular Pressure
- •
- Instruct subject to complete clinical lab collection (urinalysis, hematology, and chemistry analysis).
- Assess for adverse events

8.1.6. Double-Masked Treatment Period, Visit 6 (Month 2)

- •
- Measure vital signs
- Update concomitant medications and procedures/therapies
- •

- •
- Measure vital signs
- Update concomitant medications and procedures/therapies

- Perform slit-lamp Biomicroscopy
- Measure pupil size
- Measure Intraocular Pressure
- •
- •
- Obtain urine and perform a urine pregnancy test if the subject is a female of child-bearing potential.
- Assess for adverse events
- Exit the subject from the study.

NOTE:

If the study medication administration is discontinued, then to the extent possible, all procedures for Study Exit/Early Termination as per SoA (Table 2) will be performed on the day of early termination. Subjects who are discontinued from the study early will not be replaced.

8.1.8. Unscheduled Visits

If subject requires an unscheduled visit, procedures and assessments will be performed as needed.

8.2. Safety Assessments

8.2.1. Vital Signs

- Blood pressure and heart rate measurements will be assessed with a completely automated device. Manual techniques will be used only if an automated device is not available.
- Blood pressure and heart rate measurements should be preceded by at least 5 minutes of rest in a seated position and in a quiet setting without distractions (*e.g.*, television, cell phones).
- Temperature will be collected as per site's standard of care.

8.2.2. Clinical Safety Laboratory Assessments

• See Section 10.2 for the list of clinical laboratory tests to be performed and to the SoA for the timing and frequency.

- The investigator must review the laboratory report, document this review, and record any clinically relevant changes occurring during the study in the AE section of the CRF. The laboratory reports must be filed with the source documents. Clinically significant abnormal laboratory findings are those which are not associated with the underlying disease, unless judged by the investigator to be more severe than expected for the participant's condition.
- All laboratory tests with values considered clinically significantly abnormal during participation in the study or within 1 month after the last dose of study intervention should be repeated until the values return to normal or baseline or are no longer considered clinically significant by the investigator or medical monitor.
 - If such values do not return to normal/baseline within a period of time judged reasonable by the investigator, the etiology should be identified, and the sponsor notified.
 - All protocol-required laboratory assessments, as defined in Section 10.2, must be conducted in accordance with the laboratory manual and the SoA.
 - If laboratory values from non-protocol specified laboratory assessments performed at the institution's local laboratory require a change in participant management or are considered clinically significant by the investigator (*e.g.*, SAE or AE or dose modification), then the results must be recorded in the CRF.

8.3. Adverse Events and Serious Adverse Events

The definitions of adverse events (AEs) and serious adverse events (SAEs) can be found in Section 10.3.

AEs will be reported by the subject (or, when appropriate, by a caregiver, surrogate, or the subject's legally authorized representative).

The investigator and any qualified designees are responsible for detecting, documenting, and recording events that meet the definition of an AE or SAE and remain responsible for following up AEs that are serious, considered related to the study medication.

8.3.1. Time Period and Frequency for Collecting AE and SAE Information

All AEs will be collected from the signing of the Informed Consent Form (ICF) until subject withdrawal or the scheduled exit visit. (Note: Although AEs will be monitored for and collected prior to IP administration, the statistical data analysis will determine and summarize treatment-emergent AEs, *i.e.*, those AEs that began or worsened in severity after the first IP administration.)

All SAEs will be recorded and reported to the sponsor or designee immediately and under no circumstance should this exceed 24 hours, as indicated in Section 10.3. The investigator will submit any updated SAE data to the sponsor within 24 hours of it being available.

Investigators are not obligated to actively seek AE or SAE after conclusion of the study participation. However, if the investigator learns of any SAE, including a death, at any time after

a participant has been discharged from the study, and he/she considers the event to be reasonably related to the study intervention or study participation, the investigator must promptly notify the sponsor.

8.3.2. Method of Detecting AEs and SAEs

The method of recording, evaluating, and assessing causality of AE and SAE and the procedures for completing and transmitting SAE reports are provided in Section 10.3.

Care will be taken not to introduce bias when detecting AEs and/or SAEs. Open-ended and non-leading verbal questioning of the participant is the preferred method to inquire about AE occurrences.

8.3.3. Follow-up of AEs and SAEs

After the initial AE/SAE report, the investigator is required to proactively follow each participant at subsequent visits/contacts. All SAEs, and AEs of special interest (as defined in Section 10.3), will be followed until resolution, stabilization, the event is otherwise explained, or the participant is lost to follow-up (as defined in Section 10.3). Further information on follow-up procedures is provided in Section 10.3.

8.3.4. Regulatory Reporting Requirements for SAEs

- Prompt notification by the investigator to the sponsor of a SAE is essential so that legal obligations and ethical responsibilities towards the safety of participants and the safety of a study intervention under clinical investigation are met.
- The sponsor has a legal responsibility to notify both the local regulatory authority and other regulatory agencies about the safety of a study intervention under clinical investigation. The sponsor will comply with country-specific regulatory requirements relating to safety reporting to the regulatory authority, Institutional Review Boards (IRB)/Independent Ethics Committees (IEC), and investigators.
- For all studies investigator safety reports must be prepared for suspected unexpected serious adverse reactions (SUSAR) according to local regulatory requirements and sponsor policy and forwarded to investigators as necessary.
- An investigator who receives an investigator safety report describing a SAE or other specific safety information (*e.g.*, summary or listing of SAEs) from the sponsor will review and then file it along with the Investigator's Brochure and will notify the IRB/IEC, if appropriate according to local requirements.

8.3.5. Pregnancy Testing, Monitoring, and Reporting

8.3.5.1. Pregnancy Testing

If the subject is a woman of child-bearing potential urine samples will be collected for pregnancy tests at screening and prior to IP administrations as specified in the SoA (Table 2). Samples will be analyzed at the site with results available prior to administration of IP.

8.3.5.2. Pregnancy Monitoring and Reporting Procedures

Pregnancy in female subjects and female partners of male subjects will be monitored starting from screening through the End of study duration/Exit/Early Termination visit.

8.3.6. Adverse Events of Special Interest

8.4. Treatment of Overdose

The intervention in this study is a topical ophthalmic solution. Overdose of study medication is not anticipated. In case of any concerns regarding potential overdose, the Medical Monitor should be consulted.

8.5. Pharmacokinetics

Not applicable.

8.6. Pharmacodynamics

Not applicable.

8.7. Genetics

Not applicable.

8.8. Biomarkers

Not applicable.

8.9. Immunogenicity Assessments

Not applicable.

8.10. Health Economics/Medical Resource Utilization

Not applicable.

9. STATISTICAL CONSIDERATIONS

This section outlines the topics related to the statistical methods used in the design and analysis of the study. A more detailed description of all the analyses and methods is provided in the statistical analysis plan (SAP).

9.1. Statistical Hypotheses

The primary endpoint is change from baseline in binocular distance-corrected near visual acuity (DCNVA) at Month 2.

9.2. Sample Size Determination

Based on the feasibility of conducting the trial, a total of approximately 75 subjects will be randomized into a 2:2:1 ratio to 0.1% STN1013600, 0.3% STN1013600, and placebo arms. That is, an approximately 30 subjects and 15 subjects will be randomized into each of STN1013600 treatment arms and placebo arm, respectively.

9.3. **Populations for Analyses**

9.3.1. Safety Population

The Safety Population will include all randomized subjects who received at least one dose of the study medication.

9.3.2. Full Analysis Set

The Full Analysis Set (FAS) will include all randomized subjects who received at least one dose of study medications and provided at least one post-baseline efficacy measurement.

9.3.3. Per-Protocol Set

Then Per-Protocol Set (PPS) is a subset of the FAS, restricted to the subjects who fulfill the protocol in terms of the eligibility, medications, and outcome measurement.

9.4. Statistical Analyses

The statistical analysis plan will be finalized prior to database lock, and it will include a more technical and detailed description of the statistical analyses described in this section. This section is a summary of the planned statistical analyses of the most important endpoints including primary and key secondary endpoints.

9.4.1. General Considerations

9.4.2. Handling of Missing Values

For medical events including AEs and medical history, completely or partially missing onset and resolution dates will be imputed in a conservative fashion to be detailed in the SAP. Similar rules will be followed to impute the completely or partially missing start and end dates of nonstudy medications.

9.4.3. Primary Endpoint

The primary efficacy endpoint is change from baseline in binocular DCNVA at Month 2.

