10.4.3. Objective Refraction

10.4.4. Subjective Refraction (Manifest Refraction)

10.4.5. Distance Corrected Near Visual Acuity (DCNVA)

The distance corrected near visual acuity (DCNVA) will be measured in right eye, left eye and both eyes at all visits using the distance manifest refraction. The total number of letters at 40 cm will be recorded. Refer to Visual Acuity Manual of Procedures for details of the visual acuity assessments.

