### Figure 1: Study Design Diagram

\* On Day 1, subject should administer 1 dose of assigned medication after study visit at  $20:00 \pm 60$  min. BID dosing starts from Day 2 through Month 2.

This study will consist of a Screening Period of up to 15 days, followed by a 2-month Treatment Period and subsequently a 1-month Treatment-free follow-up Period.

At Visit 1 (Screening), subjects will be screened against the inclusion and exclusion criteria and if subject meets all eligibility criteria, subjects will proceed to Visit 2 (Baseline).

Per study design, subjects who qualify per eligibility criteria will be treated bilaterally (both eyes).

The study eye will be the eye that qualifies with the worse DCNVA per eligibility criteria at Visit 2. If both eyes have the same DCNVA, the right eye will be designated as the study eye.

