# **3.3.** Sample Size Determination

The sample size of this study is not based on any statistical power calculation due to the exploratory nature of the study and limited knowledge of the treatment effect of study medications. Based on the feasibility of conducting the trial, a total of approximately 75 subjects will be randomized into a 2:2:1 ratio to 0.1% STN1013600, 0.3% STN1013600, and placebo arm. That is, approximately 30 subjects and 15 subjects will be randomized into each of STN1013600 treatment arms and placebo arm, respectively.

Assuming a difference in mean change in DCNVA at Month 2 of 0.08 logMAR, or 4 ETDRS letters between STN1013600 group and placebo group with a standard deviation of 0.12 logMAR or 6 ETDRS letters based on literature data (Korenfeld et al., 2021), the primary analysis with 30 subjects in treatment arm and 15 subjects in control arm will achieve at least 81.5% power to detect such difference. The power calculation for the primary analysis is described in detailed in Section 12.2.

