#### Table 2: Assessment Schedule (Continued)

a Informed Consent Form must be signed and dated before study procedures are performed.

b NAVQ and SANDE questionnaires are to be performed at the beginning of the study visit, in the order reflected on Schedule of Assessments Table.

c During screening, cycloplegic refraction (objective refraction with dilation) should be performed; At visit 7 objective refraction can be performed with or without cycloplegia.

d DCNVA, and BCDVA assessments should be performed on OD, OS, and OU.

g Dilated ophthalmoscopy required at Screening and Exit visits.

h Urine pregnancy test (women of childbearing potential only) may be repeated at each visit as per request of IRB/IECs or at the Investigator's discretion.

i Only patients fulfilling eligibility criteria will be enrolled and receive the study medication.

j Dispense medication compliance diaries with when study medication is dispensed and instruct subjects on the proper completion of the diary. Collect paper diaries at specified visits and review for accuracy and completeness. Dosing for randomized subjects on Visit 2 (Day 1/Baseline) is after the study visit in the evening  $(20:00 \pm 60 \text{ min})$ , and Day 2 through Month 2 is daily BID  $(08:00 \pm 60 \text{ min})$  and  $20:00 \pm 60 \text{ min})$ . Re-educate the subject on diary completion and/or medication instillation procedures as needed.

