#### 8.1.2. Baseline Score

The *baseline score* is the observed measurement at Visit 2 (Baseline, Day 1). If a baseline score is missing, the last observed measurement or derived score prior to the first dose of study medication will be used to impute the baseline score.

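### The Screening DCNVA reading is collected before dosing but left out of the MMRMs in SAP 8.2.3 and 8.3.1; adding it as a second baseline covariate would recover a modest amount of precision.

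*Protocol*

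**What the plan says.** Protocol 9.4.3 names the endpoint ("The primary efficacy endpoint is change from baseline in binocular DCNVA at Month 2") without defining baseline. SAP 8.1.2 does: the baseline score "is the observed measurement at Visit 2 (Baseline, Day 1)", and "If a baseline score is missing, the last observed measurement or derived score prior to the first dose of study medication will be used" in its place.

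Two pre-dose readings exist. Under Protocol 10.4.5, DCNVA "will be measured in right eye, left eye and both eyes at all visits using the distance manifest refraction", and a note to the SAP assessment schedule says "DCNVA, and BCDVA assessments should be performed on OD, OS, and OU". Both Screening and Visit 2 carry the test. The SAP's design figure puts the first dose after both: "On Day 1, subject should administer 1 dose of assigned medication after study visit". The gap is bounded: "This study will consist of a Screening Period of up to 15 days". Inclusion criterion 3 (Protocol 5.1) sets the same limit at both visits, 70 letters or worse at 40 cm.

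The primary analysis (SAP 8.2.2) compares mean changes with a power prior on the control mean and names no covariate. The 8.2.3 sensitivity MMRM and the 8.3.1 MMRMs adjust for baseline, meaning the single Visit 2 value.

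**The concern.** A letter count has reading error. A model that adjusts for one reading corrects only partly for where the subject started; a second reading of the same quantity improves the correction without another visit, test or patient.

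This matters most in 8.2.3. That model is the plan's check on the primary result when the historical control and the trial's placebo arm disagree, so it has to stand without borrowed data, on about 15 placebo subjects. Sample size was set by feasibility, so precision has to come from the analysis. The same applies to the study-eye and binocular DCNVA models in 8.3.1.

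**Working it through.** **Inputs from the SAP.** Difference 4 letters, SD of change 6 letters, 30 vs 15 subjects, stated power at least 81.5% (3.3, beginning "Assuming a difference in mean change in DCNVA at Month 2 of 0.08 logMAR, or 4 ETDRS letters"). Decision rule: posterior probability above 0.95 (8.2.2). Historical control: n = 23, mean change 4.25, SD 4.35 letters (8.2.1).

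**Assumptions.** Reading SD *s* and between-subject SD *B* are given nowhere. I use *s* = 2 and *s* = 4.35/√2 = 3.08. The second is a ceiling: it treats all historical placebo change as reading error and takes that error to be similar here. *B* runs from 4 to 8 letters. Errors are independent with equal SD.

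**The plan's own power.** Without borrowing, the 0.95 rule equals a one-sided 0.05 test: power = Φ(4/√(36 × (1/30 + 1/15)) − 1.645) = Φ(2.108 − 1.645) = 67.8%. The borrowing weight *w* is not in the text available to me, so 81.5% cannot be reproduced directly. With prior variance 4.35²/(23*w*) and a true placebo mean equal to history, *w* = 0.211 gives 81.5%. With a prior SD of 6, *w* of about 0.40 fits equally well.

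**Covariate gain.** The Month 2 score has variance *v* = *B*² + 36 − *s*², which keeps the variance of change from Visit 2 at 36. Residual variance is:

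- adjusting for Visit 2 only: V1 = *v* − *B*⁴/(*B*² + *s*²)
- adjusting for both readings: V2 = *v* − *B*⁴/(*B*² + *s*²/2)

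Example, *s* = 2 and *B* = 4: *v* = 48; V1 = 48 − 256/20 = 35.20; V2 = 48 − 256/18 = 33.78.

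| *s* | *B* | V1 | V2 | Reduction | Power, V1 to V2 | Gain (points) |
|---|---|---|---|---|---|---|
| 2 | 4 | 35.20 | 33.78 | 4.0% | 68.7% to 70.2% | 1.6 |
| 2 | 8 | 35.76 | 33.94 | 5.1% | 68.1% to 70.1% | 2.0 |
| 3.08 | 4 | 32.48 | 30.19 | 7.1% | 71.7% to 74.4% | 2.7 |
| 3.08 | 8 | 34.78 | 30.94 | 11.0% | 69.1% to 73.5% | 4.4 |

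Power uses the formula above with V in place of 36. It treats the Month 2 contrast as a single-visit adjusted comparison, a fair approximation to the MMRM with the under 5% missing data reported in SAP 10.2.

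**Averaging the two readings in the primary change score instead.** The variance of change falls from 36 to 36 − *s*²/2: 34.0 at *s* = 2 and 31.27 at *s* = 3.08. At *w* = 0.211, power rises from 81.5% to 83.0% and 85.2%.

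If subjects gain *d* letters from practice between Screening and Visit 2, every change in this trial rises by *d*/2, but the prior mean stays at 4.25. At *s* = 3.08:

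- Prior precision is 0.211 × 23/4.35² = 0.257 and data precision is 15/31.27 = 0.480, so history gets weight 0.257/0.737 = 0.349. The control mean is pulled down by 0.349 × *d*/2 = 0.17*d*, in favour of active drug.
- The observed difference must exceed 1.645 × √(31.27/30 + 1/0.737) = 2.55. Its sampling SD is √(31.27/30 + 0.651² × 31.27/15) = 1.39.
- The false-positive rate is 3.3% at *d* = 0, 5.7% at *d* = 2 and 9.1% at *d* = 4.

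**The case against.** The strongest case against is that nothing here is wrong. A Day 1 pre-dose baseline is explicit and applies alike to every arm; the study is an exploratory Phase IIa; the gain is small and rests on an error SD that nobody has stated. That stands, and it limits the point to efficiency. It is also fair that a covariate in the mixed models leaves the primary analysis in 8.2.2 exactly as it is.

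Three stronger readings are tempting, and the documents support none of them.

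- **That the single baseline costs the trial up to about 11 points of power.** That figure (67.8% to 78.5%) needs an averaged baseline, no borrowing, and a reading SD of 6/√2 = 4.24, meaning that the whole planning variance is reading error. The historical SD of 4.35 points to at most 3.08, and the planned analysis borrows.
- **That the plan itself treats the two readings as interchangeable.** The fallback in 8.1.2 is a contingency for a missing value. Screening may be up to 15 days earlier and includes cycloplegic refraction, and the available text does not show its order relative to DCNVA. Differing conditions or correlated errors would shrink the gain.
- **That the primary change score should therefore use the average.** Under the assumptions above this adds about 1.5 to 4 points. However, SAP 8.2.1 chose the historical study because its endpoint matched, and a practice effect would use up part of the margin that SAP 10.2 sought with the 0.95 threshold.

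The covariate route avoids the last problem, because endpoint and prior stay as they are. It also largely meets the second: if Screening is less informative, its fitted coefficient shrinks.

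**Conclusion.** The point holds as a modest, low-cost improvement to the DCNVA mixed models. A pre-dose reading of the same measure goes unused. Including it lowers residual variance by about 4-5% at a reading SD of 2 letters and 7-11% at the 3.08 ceiling, worth roughly 1.5 to 4.5 points of power in an unborrowed comparison beyond adjustment for Visit 2. These figures depend on assumed values of *s* and *B* and on independent, equal reading errors; the upper end is a ceiling rather than an expectation. A reader should not infer that the primary analysis is biased or that its stated power is wrong on this account.

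**What to change.** In SAP 8.2.3, add Screening binocular DCNVA as a second baseline covariate beside the Visit 2 value. In 8.3.1, do the same in the two DCNVA models: binocular Screening reading for the binocular model, and for the study-eye model the Screening reading of the eye designated at Visit 2. State what happens if either reading is missing. Keep change from Visit 2 as the endpoint, and leave 8.2.2, eligibility, stratification and study-eye selection unchanged.

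The cost is a sentence in each section, one derived variable and about one degree of freedom per model. It should be written in before unmasking. Averaging the readings for the primary change score is not recommended unless the sponsor first confirms how the historical study defined baseline and examines, on masked data, the shift from Screening to Visit 2.
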